APPENDIX 6. CONTINGENT STUDY COHORTS IN CHECKPOINT INHIBITOR THERAPY NAÏVE POPULATIONS

In the event that results in the initial study cohorts are of high interest for efficacy, one or more cohorts in patients who have not previously received checkpoint inhibitor therapy (CIT-naïve) may be added to the study. Decisions for implementation of additional cohorts in the study will be made in collaboration with the Investigators and documented for Regulators and Institutional Review Boards by an Administrative Letter to Investigators.

Based on the evolving treatment landscape of urothelial carcinoma and early efficacy and safety results from active study cohorts, and in consult with Investigators, both Cohort 5 and Cohort 6 described in this appendix were implemented by an Administrative Letter dated May 2019.

The following lists sections of the main protocol and describes any changes to be implemented in cohorts of CIT-naïve patients.

Study Objectives – See main protocol.

Study Endpoints – See main protocol.

Study Design – Unchanged with the exception of the description of the populations to be enrolled into new cohorts. The population will be stratified into 2 cohorts:

- Cohort 5: Patients who have not previously received an anti-PD-(L)1, and who were previously treated with a platinum-based chemotherapy.
- Cohort 6: Patients who have not previously received an anti-PD-(L)1, and considered ineligible for platinum-based chemotherapy.

Enrollment Criteria – See main protocol (inclusion and exclusion criteria changes specific to Cohorts 5 and 6 under [Appendix 6](#) are noted as such in Section [4.1](#) and Section [4.2](#)).

Study Assessments and Procedures – See main protocol.

Statistical Design – Changes to hypothesis and sample size.

Hypothesis and Sample Size

The ORR using nivolumab in the population of advanced/metastatic urothelial carcinoma who have not previously received treatment with a checkpoint inhibitor therapy is assumed to be 20% (p_0); thus, this rate is considered uninteresting. The target ORR using sitravatinib in combination with nivolumab in this study population is 40% (p_1). Stage 1 of enrollment will include approximately 24 evaluable patients in each cohort. Patients

included in the evaluable population will have received treatment with both sitravatinib and nivolumab and will have at least one on-study disease assessment prior to discontinuation; patients who discontinue treatment due to adverse events or withdrawal of consent prior to the first on-study disease assessment will not be included in the evaluable population. With exactly 24 evaluable patients at Stage 1, if at least 6 patients have Objective Responses, enrollment of 21 additional evaluable patients is needed in the treatment cohort, for a total sample size of 45 evaluable patients. If at least 14 Objective Responses are observed in a treatment cohort, further investigation may be warranted. If the true ORR is 20% (null hypothesis), the probability of early termination during the study is 0.66; the Type 1 error is equal to 0.0483 and the power is equal to 0.9001.

The exact stopping rules for both cohorts will be calculated based on the Predictive Probability Design, once the exact number of patients evaluable at Stage 1 is known. The aim is to include approximately 24 evaluable patients at Stage 1. The Sponsor retains the option to take more than one look at the data when making decisions based on the PPD method to expand cohorts.

APPENDIX 7. EVALUATION OF THE PHARMACOKINETICS OF SITRAVATINIB IN PATIENTS WITH RENAL IMPAIRMENT

In the event results in initial patient cohorts enrolled in this study or results emerging from other ongoing clinical trials of sitravatinib are of high interest for efficacy, this evaluation of the pharmacokinetics of sitravatinib in patients with renal impairment may be implemented. These data are a necessary component in the successful development of a new cancer therapy. The fact that many patients with advanced or metastatic urothelial carcinoma have or will develop renal impairment identifies this study as an appropriate situation in which to gather these data. A subset of study sites will participate in this evaluation; it is optional for both study sites and individual patients. The decision to implement this aspect of the study will be documented for Regulators and Institutional Review Boards by an Administrative Letter to Investigators.

The evaluation of the PK of sitravatinib in patients with renal impairment was implemented by an Administrative Letter dated December 2018.

With the introduction of cohorts evaluating sitravatinib in combination with pembrolizumab and enfortumab with protocol Version 4.0, and in an effort to control for confounders, the evaluation of the PK of sitravatinib in patients with renal impairment will only apply to Cohorts 1 through 8 where the study treatment is sitravatinib in combination with nivolumab.

The eligibility criteria for this study allow enrollment of patients having renal impairment categorized as mild or moderate, defined as estimated GFR 30-59 mL/min and 60-89 mL/min, respectively, using the CKD-EPI equation ([Appendix 2](#)). Upon implementation of this study appendix, the evaluation of the PK of sitravatinib in at least 6 patients each having no renal impairment, mild renal impairment or moderate renal impairment at enrollment will be undertaken. Consenting patients with no, mild or moderate renal impairment enrolling at selected study sites will substitute blood sample collection over a 24-hour period following sitravatinib dosing on Day 1 and Day 15 (± 2 days) of treatment as described in [Table 13](#), rather than the sparse PK sampling schedule described for Day 1 and Day 15 in [Table 2](#). All other PD biomarker and ECG assessments described in [Table 2](#), as well as sparse PK sampling after Cycle 1, will be performed in the sub-study population. On the days of PK sampling, patients should delay taking the daily sitravatinib dose until the pre-dose PK sample has been collected in the clinic. PK blood samples will each collect 4 mL of blood.

Table 13: Substitute Day 1 and 15 Sitravatinib PK Sample Schedule During Renal Impairment Sub-study³

	Cycle 1 Day 1 and Again Cycle 1 Day 15 (± 2 days)						
Collection Time and Allowable Window	Pre-dose (-0.5-0 hour)	30 min (± 10 min)	2 hour (±15 min)	4 hour (±30 min)	6 hour (±30 min)	8 hour (±30 min)	24 hour (±2 hours)
PK Sample ^{1, 2}	X	X	X	X	X	X	X

- 1 Scheduled vital signs and triplicate ECGs precede PK sample collection in all cases. Sitravatinib dosing and sampling should precede nivolumab infusion.
- 2 In addition to the scheduled samples, an unscheduled PK blood sample should be drawn before a daily sitravatinib dose (trough sample) in the event of any of the following events: 1) as soon as possible after an SAE, 2) at a clinic visit at least one week following a dose modification of the investigational agent, and 3) as soon as possible after renal function declines by one Stage as defined in [Appendix 2](#), if the patient continues study treatment.
- 3 See [Table 2](#) for all other PD biomarker and ECG assessments, as well as sparse PK sampling after Cycle 1, that must also be performed.

PK concentration and parameter data will be descriptively derived and displayed. A descriptive comparison to data collected in other patients within this study and other studies within the sitravatinib program will be conducted using AUC_{0-t} , $AUC_{(0-\infty)}$, C_{max} , T_{max} , $t_{1/2}$, and steady state PK exposure parameters. Descriptive statistics will be used to summarize patient characteristics, treatment administration and safety variables. Details of this analysis will be provided in the PKAP.

APPENDIX 8. CONTINGENT STUDY COHORTS IN PATIENTS PREVIOUSLY RECEIVING TREATMENT WITH AN ANTIBODY-DRUG CONJUGATE

In the event that results in the initial study cohorts are of high interest for efficacy, one or more cohorts in patients with documented disease progression on or after a PD-(L)1 checkpoint inhibitor therapy and an antibody-drug conjugate (ADC; e.g. enfortumab vedotin, sacituzumab govitecan), in any order or in combination together. Decisions for implementation of additional cohorts in the study will be made in collaboration with the Investigators and documented for Regulators and Institutional Review Boards by an Administrative Letter to Investigators.

Based on the evolving treatment landscape of urothelial carcinoma in particular with the clinical activity of ADCs, and early efficacy and safety results from active study cohorts, and in consult with Investigators, both Cohort 7 and Cohort 8 described in this appendix were implemented by an Administrative Letter dated September 2019.

The following lists sections of the main protocol and describes any changes to be implemented in cohorts of patients that have received checkpoint inhibitor and ADC therapy.

Study Objectives – See main protocol.

Study Endpoints – See main protocol.

Study Design – Unchanged with the exception of the description of the populations to be enrolled into new cohorts. The population will be stratified into 2 cohorts:

- Cohort 7: Patients with documented disease progression on or after a previous anti-PD-(L)1 and ADC (in combination or separately, and in any order), and who were previously treated with a platinum-based chemotherapy..
- Cohort 8: Patients with documented disease progression on or after a previous anti-PD-(L)1 and ADC (in combination or separately, and in any order), and considered ineligible for platinum-based chemotherapy.

Enrollment Criteria – See main protocol (inclusion and exclusion criteria changes specific to Cohorts 7 and 8 under [Appendix 8](#) are noted as such in Section 4.1 and Section 4.2).

Study Assessments and Procedures – See main protocol.

Statistical Design – Changes to statistical design, hypothesis and sample size.

Hypothesis and Sample Size

The ORR using taxanes in the population of advanced/metastatic urothelial carcinoma who have previously received treatment with a checkpoint inhibitor therapy and ADC is assumed to be 10%; thus, this rate is considered uninteresting. The design for Cohort 7 and Cohort 8 will utilize a 95% confidence interval to exclude an ORR of 10%. Assuming sitravatinib in combination with nivolumab treatment will result in an ORR of at least 25% in this treatment setting, a sample size of approximately 55 evaluable patients would be sufficient for the lower bound of a 2-sided 95% confidence interval (Clopper-Pearson method) to exclude an ORR of 10%.

The design will include a non-binding stopping rule for futility derived using East[®] software v6.5 to control the Type 2 error rate of 0.117. The Type 2 error spending function is based on the Rho family with parameter 2.0. The futility analysis will be conducted when approximately 17 evaluable patients (approximately 30% of the total number of patients) are available for the response assessment. The futility bound will be 1 or fewer observed responses among the first 17 patients.

APPENDIX 9. CONTINGENT STUDY COHORTS EVALUATING SITRAVATINIB COMBINATION WITH A CHECKPOINT INHIBITOR AND AN ANTIBODY-DRUG CONJUGATE

In the event that results in the initial study cohorts are of high interest for efficacy, one or more cohorts in patients for treatment with sitravatinib in combination with pembrolizumab and enfortumab may be added to the study. Decisions for implementation of additional cohorts in the study will be made in collaboration with the Investigators and documented for Regulators and Institutional Review Boards by an Administrative Letter to Investigators.

Based on the evolving treatment landscape of urothelial carcinoma in particular with the clinical activity of ADCs, and early efficacy and safety results from active study cohorts, and in consult with Investigators, Cohort 9 described in this appendix is considered implemented of this protocol Version 4.0. Cohort 10 also described in this appendix is pending implementation.

The following lists sections of the main protocol and describes any changes to be implemented in cohorts of patients that will receive treatment with sitravatinib in combination with pembrolizumab and enfortumab.

Background and Rationale – See main protocol.

Study Objectives – See main protocol.

Study Endpoints – See main protocol.

Study Design – Design details specific to Cohort 9 (including lead-in dose escalation and dose expansion portions) and Cohort 10 under [Appendix 9](#) are described below including description of the populations to be enrolled into these contingent cohorts evaluating the triple combination of sitravatinib, pembrolizumab and enfortumab, the study design and dose-limiting toxicities (DLTs) as applicable.

Initially, the lead-in dose escalation portion of Cohort 9 will evaluate sitravatinib administered in combination with pembrolizumab and enfortumab in patients who have previously received a PD-(L)1 checkpoint inhibitor and a platinum-based chemotherapy. If a tolerable dose is identified for sitravatinib in combination with pembrolizumab and enfortumab, the recommended dose regimen of sitravatinib in combination with pembrolizumab and enfortumab may be further evaluated in as many as 2 populations including in patients who have previously received a PD-(L)1 checkpoint inhibitor and a platinum-based chemotherapy (dose expansion portion of Cohort 9), and in patients with previously untreated locally advanced or metastatic urothelial cancer (Cohort 10). Depending on the results in previous cohorts, only one or more of Cohort 9 and Cohort 10 may be implemented. Description of the populations to be enrolled into Cohort 9 and Cohort 10 evaluating the triple combination of sitravatinib, pembrolizumab and enfortumab are described below.

- Cohort 9 (including lead-in dose escalation and dose expansion portions): Patients who have previously received a PD-(L)1 checkpoint inhibitor and a platinum-containing chemotherapy.
- Cohort 10: Patients with previously untreated unresectable, locally advanced or metastatic urothelial cancer.

Lead-In Dose Escalation Portion of Cohort 9 Evaluating Sitravatinib in Combination with Pembrolizumab and Enfortumab

This portion of the study will begin with the lead-in dose escalation portion of Cohort 9 of up to three dose levels of sitravatinib in combination with up to two dose levels of pembrolizumab and enfortumab combination regimen, in patients who have previously received a PD-(L)1 checkpoint inhibitor and a platinum-based chemotherapy. Sitravatinib starting dose levels using the malate formulation are shown in [Table 14](#), whereas the starting doses for pembrolizumab and enfortumab are shown in [Table 15](#). Dosing will begin at 35 mg QD of sitravatinib in combination with the recommended doses of pembrolizumab and enfortumab combination regimen. This starting dose for sitravatinib represents three dose levels below the dose administered as a single agent and in combination (with nivolumab) Phase 2 and 3 trials. Dose Level 3 in [Table 14](#) is the dose used in single agent and combination Phase 2 and 3 trials. The starting doses for pembrolizumab and enfortumab (labeled as Dose Level 1 in [Table 15](#)) represent the recommended doses from the EV-103 Phase 2 trial and the EV-302 Phase 3 trial of pembrolizumab and enfortumab used in combination ([Rosenberg-2020](#); [Hoimes-2019](#)). It is of note that the EV-302 Phase 3 trial also uses these recommended doses of pembrolizumab and enfortumab in the triple combination investigation arm combining pembrolizumab and enfortumab with the platinum-chemotherapy agents cisplatin or carboplatin. In addition, a dose de-escalation step for enfortumab may be undertaken as appropriate (labeled as Dose Level -1 in [Table 15](#)). Throughout the study, pembrolizumab and enfortumab will be administered in accordance with approved labeling. Guidance for adverse event management and associated pembrolizumab treatment modifications are provided in product labeling.

Table 14: Sitravatinib Starting Dose Levels for Lead-In Dose Escalation Cohort 9 (Malate Formulation)

Sitravatinib Dose Level	Sitravatinib Daily Dose
1	35 mg PO QD
-2 ¹	50 mg PO QD
2	70 mg PO QD
3	100 mg PO QD

Abbreviations: PO = orally; QD = once daily.

1 The 50 mg dose level will be enrolled only if de-escalation is needed after assessment of the next higher dose level (70 mg).

Table 15: Pembrolizumab and Enfortumab Dose Levels

Combination Regimen Dose Level	Pembrolizumab ¹	Enfortumab ¹
-1 ²	200 mg IV Q3W	1 mg/kg IV on days 1 and 8 of Q3W
1	200 mg IV Q3W	1.25mg/kg IV on days 1 and 8 of Q3W

Abbreviations: IV = intravenous; Q3W = every 3 weeks.

- 1 Pembrolizumab and enfortumab should be administered according to USPI and standard care.
- 2 The 1 mg/kg dose level of enfortumab will be enrolled only if de-escalation is needed after assessment of the next higher dose level (1.25 mg/kg).

Dose-Limiting Toxicities (DLTs) in Cycle 1 for the Lead-In Dose Escalation Portion of Cohort 9

DLTs are only defined for patients in the lead-in dose escalation portion of Cohort 9. The definition of DLT for the purpose of dose escalation decisions includes any of the following events considered to be causally related to treatment with sitravatinib in combination with pembrolizumab and enfortumab that occurs from Cycle 1 Day 1 through pre-dose Cycle 2 Day 1:

Hematological DLTs:

- Grade 4 neutropenia, if it lasts more than 7 days.
- \geq Grade 3 febrile neutropenia.
- \geq Grade 3 neutropenia with significant clinical sequelae.
- Grade 4 thrombocytopenia.
- Grade 3 thrombocytopenia associated with clinically significant bleeding.
- Any requirement for a platelet transfusion.
- Grade 4 anemia unexplained by underlying disease.

Non-hematological DLTs:

- \geq Grade 4 infusion related reaction.
- Grade 3 infusion related reaction that does not resolve within 24 hours.
- Any \geq Grade 4 non-hematological toxicity.
- Grade 3 hypertension that cannot be controlled with medical therapy, including:

- Severe hypertension with systolic blood pressure ≥ 180 mmHg or diastolic blood pressure ≥ 120 mmHg, on more than one occasion.
- Sustained uncontrolled hypertension, with systolic blood pressure ≥ 160 mmHg (but < 180 mmHg) or diastolic blood pressure ≥ 100 mmHg (but < 120 mmHg) lasting for ≥ 14 days or causing treatment delay for ≥ 4 days.
- Other Grade 3 non-hematologic toxicity lasting for > 3 days despite optimal supportive care, with the following exceptions:
 - Endocrine disorder (thyroid, pituitary, and/or adrenal insufficiency) that can be effectively managed with hormone replacement therapy.
 - Fatigue that persists for ≤ 7 days.
 - Rash that resolves to Grade ≤ 1 within 3 weeks.
 - Tumor flare (defined as local pain, irritation, or rash localized at sites of known or suspected tumor).
- Grade 2 pneumonitis or colitis that does not resolve to \leq Grade 1 as indicated by symptoms within 3 days after onset of the event despite optimal medical management with or without corticosteroids.
- \geq Grade 3 non-hematological laboratory abnormalities with clinical consequences that do not resolve within 24 hours.
- ALT > 3 x ULN with bilirubin > 2 x ULN.
- Any other related toxic effect during the first 3 weeks may be assessed as a DLT if, upon review by the Investigators and Sponsor, it is agreed that the toxicity was of sufficient severity to be considered dose limiting.
- Any toxicity that requires suspension of sitravatinib for more than 1 week.
- A patient did not receive at least 1 dose of pembrolizumab and at least 2 doses of enfortumab up to and including Cycle 2 Day 1 due to tolerability issues (i.e., other related AEs not attributed as DLTs).

Patients from the lead-in dose escalation portion of Cohort 9 are considered DLT evaluable if they experience a DLT during the first cycle of treatment or if they clear the DLT period. Patients who received prohibited therapy during Cycle 1 (refer to Section 5.7.2), or who did not take at least 80% of the planned dose of sitravatinib, the 1 planned dose of pembrolizumab and 2 planned doses of enfortumab in Cycle 1 will be ineligible for DLT evaluation and will be replaced unless they experience a DLT event. Initially, at least 3 patients will be enrolled at each new dose level. The first patient to be treated at

each new dose level will be observed for at least one week prior to enrollment of subsequent patients at that dose level. Decision making for dose level expansion and dose escalation or de-escalation will be in accordance with the mTPI-2 method (Dose-Finding Spreadsheet presented in [Appendix 11](#)), and will be made in collaboration with the Investigators and documented for Regulators and Institutional Review Boards by an Administrative Letter to Investigators. To ensure sufficient patient experience at the dose regimen to be used in the dose expansion portion of Cohort 9 and contingent Cohort 10, enrollment at any dose regimen under consideration may be expanded to include at least 6 patients.

For the lead-in dose escalation evaluation, no dose reductions of any investigational product are allowed during Cycle 1.

Selection of Phase 2 Dose Regimen for Sitravatinib Combination with Pembrolizumab and Enfortumab (for Dose Expansion Portion of Cohorts 9 and for Cohort 10)

The RP2Ds identified in lead-in dose escalation portion of Cohort 9 will be selected for the dose expansion portion of Cohort 9 and the contingent Cohort 10. A dose regimen below the MTD may be selected.

Once RP2Ds are identified, patients from lower dose levels who continue to receive study treatment may be permitted to dose escalate to the recommended dose regimen.

Dose Expansion Portion of Cohort 9 and Contingent Cohort 10

Following completion of the lead-in dose escalation portion of Cohort 9, and in the event that a tolerable dose regimen is identified for sitravatinib in combination with pembrolizumab and enfortumab, as many as 2 cohorts will evaluate the recommended dose regimen of sitravatinib in combination with pembrolizumab and enfortumab in patients who have previously received a PD-(L)1 checkpoint inhibitor and a platinum-based chemotherapy (dose expansion portion of Cohort 9), and in patients with previously untreated locally advanced or metastatic urothelial cancer (Cohort 10).

Enrollment Criteria – See main protocol (inclusion and exclusion criteria changes specific to Cohorts 9 and 10 under [Appendix 9](#) are noted as such in [Section 4.1](#) and [Section 4.2](#)).

Study Assessments and Procedures – See main protocol.

Statistical Design – Changes to statistical design, hypothesis and sample size.

Hypothesis and Sample Size

Lead-In Dose Escalation Evaluation for Sitravatinib Combination with Pembrolizumab and Enfortumab (Cohort 9)

Up to 30 patients may be enrolled into the lead-in dose escalation portion of Cohort 9.

The mTPI-2 design ([Guo-2017](#)) will be employed in decision making of dose escalation within each regimen investigated. The mTPI-2 design is based on the following assumptions:

- the maximum tolerated dose (MTD) is the dose associated with probability of dose limiting toxicity in 30% of patients during the first treatment cycle; and
- the acceptable variance around the MTD is - 0.05 to + 0.03 (i.e., the region of the MTD is 25% to 33% incidence of dose limiting toxicity).

Refer to [Appendix 11](#) for the dose escalation decision table using the mTPI-2 method.

Dose Expansion Portion of Cohort 9 and Cohort 10

Simon 2-stage optimal designs ([Simon-1989](#)) will be used to establish stopping rules for futility for the dose expansion portion of Cohort 9 and for Cohort 10. The dose expansion portion for Cohort 9 will also include patients from the lead-in dose escalation portion of Cohort 9 who had similar starting doses to the recommended starting doses for the sitravatinib combination with pembrolizumab and enfortumab.

- For the dose expansion portion of Cohort 9, the null hypothesis for ORR is 45%; the alternative hypothesis for ORR is 70%. The first stage of patient enrollment will include 15 patients evaluable for response. If 8 or more patients achieve an objective response, enrollment will continue to approximately 35 patients; if at least 21 objective responses are observed from both stages, further investigation will be considered warranted. If the true ORR is 45% (null hypothesis), the probability of early termination during the study is 65.4%; the Type 1 error is 0.048, and the power is 90.0%.
- For Cohort 10, the null hypothesis for ORR is 45%; the alternative hypothesis for ORR is 65%. The first stage of patient enrollment will include 19 patients evaluable for response. If 10 or more patients achieve an objective response, enrollment will continue to approximately 49 patients; if at least 28 objective responses are observed from both stages, further investigation will be considered warranted. If the true ORR is 45% (null hypothesis), the probability of early termination during the study is 67.1%; the Type 1 error is 0.05, and the power is 85%.

APPENDIX 10. EXAMPLES OF PROHIBITED P-GP INHIBITORS AND STRONG CYP3A4 INHIBITORS DURING TREATMENT WITH ENFORTUMAB

Patients must have discontinued treatment with any of the following for at least 2 weeks prior to the first dose date of enfortumab. There could also be additional new drugs and marketed drugs that could be identified as inducers/inhibitors with continued research. Use of any concomitant medication known to be a P-gp inducer/inhibitor and/or a strong CYP3A4 inhibitor with enfortumab is not permitted.

Strong CYP3A4 Inhibitors	Boceprevir, clarithromycin, cobicistat, conivaptan, danoprevir/ritonavir, diltiazem, elvitegravir/ritonavir, grapefruit juice, idelalisib, indinavir/ritonavir, itraconazole, ketoconazole, lopinavir/ritonavir, mibefradil, nefazodone, nelfinavir, paritaprevir/ritonavir/ombitasvir plus dasabuvir, posaconazole, ritonavir, saquinavir/ritonavir, telaprevir, tipranavir/ritonavir, telithromycin, troleandomycin, voriconazole.
P-gp Inhibitors	Azithromycin, captopril, carvedilol, clarithromycin, conivaptan, cyclosporine, diltiazem, dronedarone, erythromycin, felodipine, itraconazole, ketoconazole, lopinavir, ritonavir, quercetin, quinidine, ranolazine, ticagrelor, verapamil.
P-gp Inducers	Avasimibe, carbamazepine, phenytoin, rifampin, St John's wort, tipranavir/ritonavir.

Note: Any additional P-gp inducers/inhibitors or strong CYP3A4 inhibitors that are identified or become commercially available while the clinical trial is ongoing are also prohibited.

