The renal impairment classification scale provided in the guidance document considers eGFR and Estimated Creatinine Clearance (CL_{Cr}). It allows for the fact that equations to calculate eGFR are evolving. In this study, eGFR will be calculated using the CKD-EPI equation with substitution of individual body surface area based on height and weight rather than use of the standardized value of 1.73 m². The following scale is a reprint from the FDA Guidance for Industry and will be used to group patients in the renal impairment substudy described in [Appendix 7](#) and in population pharmacokinetic analyses.

Classification of Renal Function Based on Estimated GFR or Estimated Creatinine Clearance			
Stage	Description	eGFR (mL/min/1.73m ²)	CL _{Cr} (mL/min)
1	Control (Normal) GFR	≥ 90	≥ 90
2	Mild Decrease in GFR	60-89	60-89
3	Moderate Decrease in GFR	30-59	30-59
4	Severe Decrease in GFR	15-29	15-29
5	End Stage Renal Disease	<15 not on dialysis or requiring dialysis	<15 not on dialysis or requiring dialysis

APPENDIX 3. MEDICATIONS OR SUBSTANCES TO BE AVOIDED OR USED WITH CAUTION DURING TREATMENT WITH SITRAVATINIB

Examples of Drugs with a Known Risk of Torsades de Pointes*

Generic Name	Brand Names (Partial List)	Drug Class	Therapeutic Use
Aclarubicin (Only on Non US Market)	Aclacin, Aclacinomycine, Aclacinon, Aclaplastin, Jaclacin	Anti-cancer	Cancer
Amiodarone	Cordarone, Pacerone, Nexterone	Antiarrhythmic	Arrhythmia
Anagrelide	Agrylin, Xagrid	Phosphodiesterase 3 inhibitor	Thrombocytopenia
Arsenic trioxide	Trisenox	Anti-cancer	Cancer (leukemia)
Astemizole (Removed from US Market)	Hismanal	Antihistamine	Allergic rhinitis
Azithromycin	Zithromax, Zmax	Antibiotic	Bacterial infection
Bepiridil	Vascor	Antianginal	Angina Pectoris (heart pain)
Cesium Chloride	Energy Catalyst	Toxin	Alternative therapy cancer
Chloroquine	Aralen	Antimalarial	Malaria
Chlorpromazine	Thorazine, Largactil, Megaphen	Antipsychotic / Antiemetic	Nausea, schizophrenia, many others
Chlorprothixene (Only on Non US Market)	Truxal	Antipsychotic	Schizophrenia
Cilostazol	Pletal	Phosphodiesterase 3 inhibitor	Intermittent claudication
Ciprofloxacin	Cipro, Cipro-XR, Neofloxin	Antibiotic	Bacterial infection
Cisapride (Removed from US Market)	Propulsid	GI stimulant	Increase GI motility
Citalopram	Celexa, Cipramil	Antidepressant, SSRI	Depression
Clarithromycin	Biaxin, Prevpac	Antibiotic	Bacterial infection
Cocaine	Cocaine	Local anesthetic	Anesthesia (topical)
Disopyramide	Norpace	Antiarrhythmic	Arrhythmia

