7.1.4 Contingent PK Evaluation in Patients with Renal Impairment

In the event results in initial patient cohorts enrolled in this study or results emerging from other ongoing clinical trials of sitravatinib are of high interest for efficacy, the evaluation of the pharmacokinetics of sitravatinib in patients with mild or moderate renal impairment may be implemented. Appendix 7 of the protocol describes the plan for this assessment. Upon implementation of this study appendix, the evaluation of the PK of sitravatinib in at least 6 patients each having mild or moderate renal impairment at enrollment will be undertaken. Details of this analysis will be provided in the PKAP.

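### Protocol Appendix 7 transposes the eGFR ranges for mild and moderate renal impairment, against the Appendix 2 scale that is to group the PK sub-study

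*Protocol*

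**What the plan says.** Evaluating sitravatinib PK in patients with renal impairment is a secondary objective (Protocol Section 2.1.2, SAP Section 6.1.2). Protocol Appendix 7 sets out the sub-study.

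- **Appendix 7, category definition.** The study admits patients with "renal impairment categorized as mild or moderate, defined as estimated GFR 30-59 mL/min and 60-89 mL/min, respectively", with eGFR from the CKD-EPI equation and a reference to Appendix 2.
- **Appendix 7, group sizes.** The next sentence calls for PK evaluation in "at least 6 patients each having no renal impairment, mild renal impairment or moderate renal impairment at enrollment".
- **Appendix 2, classification table.** Stage 2 reads "Mild Decrease in GFR 60-89 60-89" and Stage 3 reads "Moderate Decrease in GFR 30-59 30-59".
- **Appendix 2, status of that table.** "The following scale is a reprint from the FDA Guidance for Industry and will be used to group patients in the renal impairment substudy", and also in the population PK analyses.
- **SAP Section 7.1.4.** It points to Protocol Appendix 7, gives no eGFR ranges, and plans PK evaluation "in at least 6 patients each having mild or moderate renal impairment at enrollment will be undertaken". The analysis details are left to the PKAP, which is not among the documents.

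**The concern.** Two appendices of the same protocol attach opposite labels to the same two eGFR bands. The faulty sentence is current text, and it comes immediately before the sentence that sets the minimum group sizes by those labels, so it cannot be set aside as background.

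What is at stake is how a secondary PK objective is read. A renal impairment sub-study asks whether exposure changes as renal function falls. If the two labels were exchanged in the output, exposure at 30-59 mL/min would appear under mild and exposure at 60-89 mL/min under moderate, and any trend across the impaired groups would be read in the wrong direction. The sub-study was put in place by an Administrative Letter of December 2018, and the Study Summary describes it as active. Appendix 12 suspends only the entry of new patients during the pandemic. Some patients may therefore already have been assigned to groups.

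**Working it through.** No power or error rate is involved, so the check is a comparison of definitions followed by a count.

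**1. The two definitions side by side**

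| Label | Appendix 7 | Appendix 2 |
|---|---|---|
| Mild | 30-59 | 60-89 (Stage 2) |
| Moderate | 60-89 | 30-59 (Stage 3) |
| No impairment | no range given | 90 or more (Stage 1) |

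The bands are identical and only the labels are exchanged. Units do not explain it: the Appendix 2 table prints the same bands in its eGFR column and in its creatinine clearance column.

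**2. Worked cases.** A patient with eGFR 45 mL/min is mild under Appendix 7 and moderate under Appendix 2. A patient with eGFR 75 mL/min is moderate under Appendix 7 and mild under Appendix 2.

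**3. Which passage is in error.** Three places in the protocol point the same way.
- Appendix 2 names its own scale as the one that groups the sub-study.
- Footnote 2 to Table 13, inside Appendix 7, asks for an extra trough sample when renal function falls by one Appendix 2 stage. A fall from Stage 2 to Stage 3 would, in the words of Appendix 7, take a patient from moderate to mild while function worsens.
- The enfortumab background in Section 1.6.3.1 has mild as creatinine clearance above 60 to 90 mL/min and moderate as 30 to 60 mL/min, the same order as Appendix 2.

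**4. Number of patients exposed to a reversal, if Appendix 7 were followed.** There are three groups with at least 6 patients each, so at least 3 × 6 = 18 in all. The two impaired groups hold at least 2 × 6 = 12 of these. The no-impairment group is not touched.

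**5. The same number if Appendix 2 is followed.** Zero.

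**6. What does not depend on the labels**
- Eligibility: inclusion criterion 7f uses serum creatinine and a 30 mL/min floor, and neither label.
- The combined impaired range is 30-89 mL/min under both definitions.
- The minimum is 6 for each group, so exchanging the names leaves the number needed in each band unchanged.
- Sampling: Table 13 is the same for all groups.

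**7. The SAP.** Section 7.1.4 states no ranges, so it neither repeats the transposition nor resolves it. It names the mild and moderate groups and leaves out the no-impairment group that Appendix 7 requires, although SAP Section 5.0 says the plan was developed from protocol version 4.0.

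**The case against.** The strongest reply is that the protocol already contains the right rule. Appendix 2 says that its scale "will be used to group patients in the renal impairment substudy", and that eGFR for reporting is derived within the study database. On that footing, patients are grouped from derived eGFR on the Appendix 2 scale, and the Appendix 7 sentence is a slip of word order in a statement about who may enter the main study. The analysis is descriptive, so no test depends on the labels, and the PKAP, which holds the details, cannot be inspected here.

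Most of this stands. A reader might infer that the sub-study groups are in fact labelled in reverse, that every patient with eGFR 30-89 mL/min gets the wrong label, or that sites are recruiting to the wrong groups. The documents do not support any of these. The stated grouping rule is the correct one, nothing shows that the Appendix 7 wording has been applied, and the documents set a minimum per group without saying that sites fill places by label.

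Two things remain. First, the Appendix 2 reference in the faulty sentence directly follows the mention of the CKD-EPI equation, so it can be taken as a reference for the equation alone, which leaves the ranges in the sentence looking like a definition in their own right. Second, the SAP sends the reader to Appendix 7 for the plan. Someone drafting the PKAP or the report from that appendix would find an explicit and wrong definition.

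**Conclusion.** This is an internal inconsistency, and the Appendix 7 sentence is wrong as written. It is probably a drafting slip, but it is a wrong category threshold in the description of a sub-study that serves a secondary objective, so it should be corrected.

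The size depends on which passage is used. Following Appendix 7 would reverse the labels of at least 12 of at least 18 patients and report the worse renal group as mild. Following Appendix 2 would mislabel nobody. The conclusion assumes that Appendix 2 governs, as it says, and takes no position on what the PKAP contains. Who can enter, how many are needed, how they are sampled and the primary endpoint are not affected.

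The missing no-impairment group in SAP Section 7.1.4 is a separate and smaller mismatch, and it adds no weight to this point.

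**What to change.** 1. In Protocol Appendix 7, exchange the two ranges so that mild is 60-89 mL/min and moderate is 30-59 mL/min, and name Appendix 2 Stages 2 and 3 so that the reference clearly covers the categories as well as the equation.
2. Confirm that the PKAP, and any group assignments already made, use the Appendix 2 scale.
3. As a separate minor alignment, have SAP Section 7.1.4 cite the Appendix 2 stages and list the no-impairment group alongside mild and moderate.

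The cost is a one-line clarification in the protocol, one line in the SAP and a check of the PKAP. No new data are needed.
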